#### **Psychosocial Questionnaires:**

This study will employ psychosocial measures to capture the short- and long-term impacts of KFC. Specifically, validated measures of parenting confidence, relationship quality, infant bonding, and father involvement will be assessed via a set of paper or REDCap surveys administered in the NICU (short term) at baseline and the day before discharge (T-1), and at home (long term) at 2 weeks (T+14) and 4 weeks (T+30) after discharge. Each of these sets of surveys will take approximately 30 minutes to complete. At baseline, each parent will complete the Revised Dyadic Adjustment Scale (RDAS) and the Postpartum Bonding Questionnaire (PBQ). At T-1, each parent will complete the RDAS , the PBQ, and the Parenting Sense of Competence Scale (PSOC). These questionnaires will be completed on paper or directly in REDCap, depending upon the participant's preferences. Data provided on surveys completed on paper will be transferred to secure REDCap forms by study staff and destroyed within 24 hours. At T+14 and T+30, each parent will complete the RDAS, the PBQ, the PSOC, and a Father Involvement Questionnaire. These questionnaires will be completed directly in REDCap only. Each parent will complete the RDAS, the PBQ, the PSOC, and a Father Involvement

receive an email containing a link to their set of questionnaires at both post-discharge time points. All questionnaire data will be stored long term on the secure REDCap server housed by Northwestern University.

#### Wearable Sensor Data Collection:

The wearable sensor that will be used in this study can stream data continuously using near field communication (NFC) or Bluetooth technology. An encrypted laptop, iPad, or similar device will be left in the patient room and used to capture the continuous data stream from the wearable sensor. Additionally, wearable biosensors can include onboard memory, and physiologic streams may be recorded to this onboard memory until transfer to an encrypted laptop for analysis.

We have recently upgraded a new firmware version activating the ability for the sensor to continuously measure bioimpedance for respiratory rate. This function does not require any modification to the physical device itself or the adhesive. However, the bioimpedance functionality does require delivery of low amplitude sinusoidal current through the electrodes of the chest unit. The frequency of the current is 4 kHz – a frequency range used typically for human bioimpedance measurements by FDA cleared systems. The maximum current delivered is 8  $\mu$ A. The sensors with these parameters are safe to be worn by the infants for the duration of the study, which is up to 48 hours. These parameters are below commonly used body fat percentage impedance analyzers that are widely commercially available. Furthermore, bioimpedance is standard measurements in existing NICUs / PICUs leveraging the ECG electrodes that are then displayed on standard of care monitors. Commercially bioimpedance devices that are FDA approved inject currents that are 10x greater than our system (e.g. the CoVa Monitoring System 2 for continuous wearable sensing of thoracic impedance). Finally, the parameters in our sensor follow IEC 60601-1-2 guidelines for electromagnetic safety.

#### Standard of Care Data Collection:

In all patients in rooms where data from standard of care monitoring is recorded on the BedMaster system, this data will be used for comparison to data captured using the wearable sensors. In participants in rooms where this system is not available, the MediCollector system will be used to capture background data during the approximately 48-hour study.

## 3.4. Study Timeline

Activity	Duration
Study Set-up	12/2018-3/2019
Recruitment	2/2019-5/2021
Data Collection	2/2019-5/2021
Final Data Analyses + Report	12/2019-12/2021

# 4. Study Safety

## 4.1. Privacy Protections

The study team will take measures to protect the privacy and confidentiality of participants. The plan to protect patient privacy includes approaching and consenting participants in a private room. Study procedures will be done in the privacy of the patient rooms in the ICU. Study participation discussions will be limited to members of the study staff and the involved participants.

Participant data will be coded with study identifier only. All data obtained from the bedside monitors will be stored on the Azure Cloud (maintained by Data Analytics Reporting (DAR) at Lurie Children's). All data obtained using wearable sensors will be stored on an encrypted laptop and secure network for later analysis. All questionnaire responses will be collected via Research Electronic Data Capture (REDCap) hosted by Northwestern University. When preferred, parents can fill in questionnaires on paper, and these will be transferred to REDCap by study staff after collection.

To minimize the risks, only the minimum data necessary to complete the study will be collected on each study participant.

Photographs will be labeled only by study code, and will not include subject's face. Video may include the subject's face, but all videos will be scored for position and movement within 1 month of recording, and will be deleted after scoring. All photos and videos will be stored on a password protected server accessed by a password protected computer.

Only authorized personnel listed in the IRB application will have access to study data. The screening and enrollment log used contain the code link, and this file will be stored on the REDCap server and will have access limited to the study team. The link between the participants and their study identifier will be destroyed at the conclusion of this study, so all remaining data will be fully de-identified.

Data transferred to the study team by the NU electronic data warehouse for patients meeting screening criteria in the Prentice NICU will be downloaded onto the Lurie Children's Hospital server. This data file will be used for up to one week to allow the screening process to take place, then will be deleted.

Confidentiality will be maintained with all of the medical records of this study. Subject records will be kept in a locked cabinet, under the control of the Principal Investigator. The subject will also be assigned a code in the data sheets so that the records on the computer will be kept confidential.

#### **Potential Risks**

**Sensor Risks**: There is a risk of discomfort or irritation from the adhesives used with wearable, wireless biosensors. It is possible that the additional handling required to place the biosensors may be temporarily disruptive for the participants. Study staff will check on the participant at least once every 24 hours to monitor for signs of discomfort, irritation, or allergic reaction. Skin integrity will be scored according to the protocol, and the bedside team will be consulted within 1 hour for any concerns. Any adverse events or evidence of discomfort during monitoring will be recorded and the bedside team will be immediately consulted. Photographs will be taken at baseline and after study; skin changes during the period of wearable biosensor use or at subsequent time points will be documented photographically.

**Parent Questionnaire Risks**: Some questions may make parents uncomfortable or upset. It will be made clear to the parents that they do not have to answer any questions that make them feel uncomfortable or upset. The parents will be informed that they can end their participation in the study at any time

## 4.2. Discontinuation Criteria

A participant may be discontinued if the participant is unwilling or unable to tolerate the wearable sensors, saliva collection, or skin-to-skin session. Examples may include adverse reactions to the adhesive on the wearable sensors or a patient removing the wearable sensors. The bedside clinical team or family can also request discontinuation at any time. Families participating in the video monitoring can request discontinuation of the video monitoring aspect of this study at any time during the study.

# 4.3. Patient Withdrawal

Any participants withdrawn from the study will have the wearable sensors removed immediately. Any data collected prior to the withdrawal will remain a part of the study, and this data will be coded.

# 5. Statistical Analysis

## 5.1. Statistical Plan

Measurements made through clinical standard of care will be compared to the measurements recorded by the wearable sensors. Distribution checks for normality and data accuracy will be completed for each individual and for the entire study prior to all analyses. For continuous measures of physiology, 30 second epochs will be defined for each method for comparison.

Agreement and correlation of wearable biosensor measures to standard of care measures will be assessed in two ways. First, Bland–Altman plots will be created to assess agreement between each measurement system via bias and precision, which reflect the mean or average difference between two methods and the variation in these differences, respectively. Our second method consists of individual correlations between methods assessed for each person. This correlational method will supplement additional methods, and can be directly transformed to variance shared between wearable biosensor and standard of care measures, a common metric of reliability of any measure.

Formal tests of bias, precision, and correlations: While the above methods will yield useful statistics, they need to be extended to deal with the structured nature of our data. Specifically, our data are clustered, meaning that we have multiple observations within each person and multiple people in our sample, which violates standard independence assumptions inherent to many models. We propose to estimate bias and correlation/reliability using multi-level models, which yield the same statistics discussed above but account for the fact that observations taken from the same patient are more related than comparisons involving different patients.

Data will be cleaned and analyzed using IBM SPSS Statistics 20.0, unless a newer version of SPSS is available. Using repeated-measures analysis of variance (RM-ANOVA), with the study phase (pre-, during-, and post-kangaroo care) as the repeated factor, we will test differences across study phase for maternal cortisol, paternal cortisol, infant cortisol, paternal oxytocin, and paternal testosterone. We will use a two-tailed test with a 5% level of significance analysis. In addition to tracking changes over the period of kangaroo care, we will also examine within-triad correlations in cortisol for mother-father-

infants in the same family, as well as correlations between infant cortisol and father testosterone/oxytocin, and maternal cortisol and father testosterone-oxytocin.

Statistical Power: The large amount of within-person data provides incredibly high statistical power for all planned and many secondary data analyses, allowing this data set to answer all proposed questions. Previous work on power in multilevel models found greater than 99% power to detect associations with the planned observations suggested here within comparable nested designs.

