# 2.2. Outcome Measures

## 2.2.1. Primary Outcome

Primary outcome measures include heart rate (HR) and oxygen saturation (SpO2) as indicators of cardiorespiratory stability in infants before, during, and after KC and HR and HR variability (HRV) as indicators of physiologic stress in NICU parents during and after periods of KC. All of these outcomes will be measured using wearable, wireless biosensors.

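### SpO2 agreement is summarised numerically only over the whole range, so a moderate sensor error confined to infrequent low-saturation epochs could go unestimated

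*Combined protocol and SAP*

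**What the plan says.** Section 2.2.1 makes infant SpO2 part of the primary outcome: "heart rate (HR) and oxygen saturation (SpO2) as indicators of cardiorespiratory stability in infants before, during, and after KC". It adds that "All of these outcomes will be measured using wearable, wireless biosensors". It gives no threshold, desaturation count, time below a level or other summary for SpO2.

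Section 5.1 compares wearable and standard-of-care readings in 30-second epochs, in three steps:

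- "Bland–Altman plots will be created to assess agreement". Their purpose is to "assess agreement between each measurement system via bias and precision, which reflect the mean or average difference between two methods", and the sentence goes on "and the variation in these differences, respectively". Bias is thus the mean difference and precision the spread of the differences.
- "Our second method consists of individual correlations between methods assessed for each person".
- To deal with clustering, "We propose to estimate bias and correlation/reliability using multi-level models". The text says these models give the same statistics as the first two steps; the only stated extension is for repeated observations on a person.

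Nothing asks for bias or precision at different saturation levels, a check for error that changes with level, or agreement on low-saturation epochs. No acceptance limit is stated for any measure.

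**The concern.** A single bias and a single SD of differences describe a device well if its error is much the same at every level. If the error is different at low saturation and few epochs are low, the many high-saturation epochs dominate both figures. A correlation over the whole range does not isolate the low end either, and a multi-level model that adds only clustering inherits the same limitation.

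What is at stake is the reach of the agreement claim. Section 1 lists intermittent hypoxemia among the risks of preterm infants, and the wearable's SpO2 is offered as a stability indicator. Good overall agreement could be taken to show that the sensor is sound when saturation falls, which the planned numbers would not have tested.

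**Working it through.** **From the documents.** Epochs of 30 seconds are 120 per hour (Section 5.1). A two-hour session therefore has 240 epochs, and sensor wear of up to 48 hours at most 48 × 120 = 5,760 (Section 3.3). The plan states no expected bias, SD of differences, acceptance limit or saturation distribution, so there is no figure of its own to reproduce.

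**Assumed, not in the documents.** A share f of epochs is at low saturation; the wearable reads those e points too high and is unbiased elsewhere; the SD of differences is otherwise s = 2.0 points.

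**Formulas.** Pooled bias = f × e. Pooled SD = √(s² + f(1 − f)e²). Limits of agreement = bias ± 1.96 × SD.

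| f | e | Pooled bias | Pooled SD | Limits of agreement |
|---|---|---|---|---|
| – | 0 | 0 | 2.00 | −3.92 to 3.92 |
| 1% | 3 | 0.01 × 3 = 0.03 | √(4 + 0.01 × 0.99 × 9) = 2.02 | −3.93 to 3.99 |
| 3% | 4 | 0.03 × 4 = 0.12 | √(4 + 0.03 × 0.97 × 16) = 2.11 | −4.02 to 4.26 |
| 5% | 6 | 0.05 × 6 = 0.30 | √(4 + 0.05 × 0.95 × 36) = 2.39 | −4.38 to 4.98 |

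The error in the low range is 3 to 6 points in every row, while the pooled bias is at most 0.30.

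**What this can mean for single epochs.** A simulation drew low reference values uniformly from 75 to 88, drew the rest from about N(96, 2) limited to 89 to 100, and ignored clustering. With f = 2% (about 5 of 240 epochs, or 115 of 5,760) and e = 5:

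- Bias is 0.10, SD 2.12, and the limits are −4.05 to 4.25.
- Correlation, pooled over epochs rather than taken per person, falls from 0.82 to 0.75.
- The share of truly low epochs that the wearable also reads below 88 falls from 94% to about 60%. The value 88 is only the simulation's cut-off.

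**Where the planned statistics do react.** With f = 5% and e = 10, the SD rises to 2.96 and the correlation falls from 0.88 to 0.64. The gap therefore concerns moderate or infrequent errors.

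**Which remedy recovers the error.** The three table rows were simulated with the same saturation distribution and errors in both devices.

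- *Linear term for the mean of the two readings.* The predicted bias at 85% was about 0.66, 1.70 and 3.23, against true errors of 3, 4 and 6. With unequal error SDs (wearable 1.73, monitor 1.0; √(1.73² + 1.0²) = 2.0), an unbiased sensor showed a false slope of +0.09 and a false bias of about −0.9 at 85%. In the 3-point case the prediction was about −1, so its sign reversed.
- *Bias in the band below 85 of the mean of the two readings.* This gave 2.9 to 3.0, 3.9 to 4.0 and 5.9 to 6.0.

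**The case against.** The strongest reply is that the plan is richer than a bare mean difference. It includes precision, per-person correlations and Bland–Altman plots, and a plot of difference against mean is the standard display for error that changes with level. This stands in part. A reader might infer that agreement rests on one average bias; the documents do not support that, since the sentence on bias goes on to precision. But a plot yields no estimate, and with up to 5,760 epochs per infant a few low points are easy to overlook.

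Three other inferences are tempting and also unsupported:

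- *A faulty sensor would pass.* No acceptance limit exists, so nothing passes or fails. Equally, nothing would flag a modest shift in SD or correlation.
- *Low saturation is what the outcome must detect.* Section 2.2.1 sets no threshold, and hypoxemia appears only as one item in the background. If the outcome were mean SpO2 by phase, an error confined to a share f of that phase's epochs would shift the phase mean by the same small f × e (0.03 to 0.30 in the cases above).
- *This sensor over-reads at low values, or low epochs are rare.* The documents give no data on either. The figures show what could be hidden, not that anything is.

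It is also fair to say that the missing analysis could be added later from the same stored data. That keeps the point modest, but bands chosen after seeing the data would carry less weight.

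**Conclusion.** The point holds in limited form. All planned numerical summaries of SpO2 agreement are range-wide. Under the stated assumptions they would report a pooled bias of 0.03 to 0.30 points and an SD of 2.02 to 2.39 while the low-range error is 3 to 6 points. The overall figures alone therefore do not support relying on the wearable when saturation falls.

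The size rests on assumed values for the share of low epochs, the error and the SD. The consequence for the primary outcome rests on a summary measure that Section 2.2.1 leaves undefined: it is small for a phase mean, and could be substantial for a measure built on low readings. Large or frequent low-range errors would show in the planned SD and correlation.

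**What to change.** Keep the planned statistics. From the same 30-second epochs, also report SpO2 bias and limits of agreement, with intervals adjusted for clustering, in prespecified bands of the mean of the two readings. An example is below 85, 85 to below 90, 90 to below 95, and 95 or above; these are analysis bands only and carry no clinical meaning. Enter band as a categorical term in the multi-level model and let the variance differ by band. Do not rely on a single linear term for level: it understates the low-range error and can reverse its sign when the two devices have unequal error variances. Limit any claim of SpO2 agreement to the bands where it is shown.

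The cost is one model term and one table, with no new data collection. Intervals in the lowest band will be wide if few epochs fall there. If the error variances differ, some artefact will remain in the bands near the bulk of the data, and the report should say so.

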#### Kangaroo Care (KC) Intervention:

After enrollment, families will be scheduled to participate in two sessions of KC. The goal will be to schedule the KC sessions over two sequential days and at approximately the same time of day (i.e. morning, afternoon, or evening). However, if this is not possible given the parents' schedules, the sessions will be scheduled for the days and time of day that participating parents are able to visit their infant in the NICU. Each session will include two hours of continuous KC, with one day focused on Kangaroo Mother Care (KMC) and the other on Kangaroo Father Care (KFC), in a randomized order. These sessions will include continuous skin-to-skin holding of the infant by the parent, per standard of care protocol.

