#### **Physiologic Recording:**

*Infant*: Prior to the first scheduled KC session, two wearable, wireless biosensors will be placed on the infant to continuously capture physiology measures including electrocardiogram (ECG), heart rate (HR), oxygen saturation (SpO2), body temperature, respiratory rate, movement, systolic blood pressure (BP-S), and others for the duration of the study. One device will be placed on the infant's chest or back. A second device will be placed peripherally, on the infant's leg, foot, arm, or hand. The devices are encapsulated in a medical-grade silicone and will be adhered to the infant's skin using a medical-grade adhesive, similar to the adhesives standardly used in the NICU. The biosensors will be left in place for up to 48 hours, but will be checked by study staff at least once every 24 hours to ensure skin integrity and signal quality. The adhesives will be changed between uses.

**Parent:** The same type of wearable, wireless biosensor will also be used to record 4 hours of continuous physiology including ECG, HR, temperature, movement, SpO2, and others in the infant's parents. The biosensor will be placed on the parent's chest 1 hour before the start of a scheduled KC session and worn for 1 hour preceding the scheduled KC session, during the 2-hour KC session, and for 1 hour after the completion of the KC session. The biosensor will be worn by the parents for approximately 4 hours in total.

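### Section 5.1 names only patient clustering for its 30-second epochs and rests its power on within-person volume; the power claim is unsupported, and epoch-level standard errors can be too small.

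*Combined protocol and SAP*

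**What the plan says.** Section 5.1 sets the unit of analysis: "For continuous measures of physiology, 30 second epochs will be defined for each method for comparison". Agreement between sensor and standard-of-care monitor is assessed by Bland–Altman plots and by "individual correlations between methods assessed for each person". The plan recognises that such data are clustered and moves to multi-level models for formal tests. The reason it gives is that these models "account for the fact that observations taken from the same patient are more related than comparisons involving different patients". It lists no random effects, no session level and no residual covariance, and it does not mention serial correlation.

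Repeated-measures ANOVA across the three study phases is assigned to the salivary hormones only. The primary outcomes in section 2.2.1 (infant HR and SpO2 before, during and after kangaroo care; parent HR and HRV during and after it) have no phase analysis written out.

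The power paragraph says: "The large amount of within-person data provides incredibly high statistical power for all planned and many secondary data analyses". It adds a figure of more than 99%, attributed to earlier work on comparable nested designs. No reference is attached to that sentence.

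**The concern.** Neighbouring 30-second epochs from one continuous recording carry overlapping information. A patient intercept captures the fact that one infant's HR runs higher than another's. It does not capture slow drift within a recording, or phase effects and sensor-monitor slopes that differ between people. A model that ignores these counts every epoch as a nearly fresh observation when it estimates within-person quantities.

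Two things are at stake. The power statement, which is the trial's only justification of size, relies on that same counting. And the multi-level model is the only epoch-level model in section 5.1, so it is the natural candidate for the primary HR, SpO2 and HRV contrasts. In its simplest form it would be unsafe for them.

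**Working it through.** **The plan's own figure.** The power above 99% cannot be reproduced. The documents give no number of families, effect size, variance components or autocorrelation.

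**Inputs from the documents.** Epochs last 30 seconds, so 120 per hour. For parents the sensors "record 4 hours of continuous physiology", so 4 × 120 = 480 epochs: 120 before, 240 during, 120 after. "Each session will include two hours of continuous KC", which is the 240. For infants, "The biosensors will be left in place for up to 48 hours", so up to 48 × 120 = 5,760 epochs. The 5% two-sided level is stated in the hormone paragraph.

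**Assumptions, not in the documents.** Lag-1 autocorrelation ρ of 0.5, 0.8 or 0.9 under an AR(1) process; 10 to 40 persons; between-person SD of 0.5 to 1 times the residual SD.

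**Formulas.** True SE divided by the SE computed under independence:
- mean or slow within-person contrast: √[(1+ρ)/(1−ρ)], slightly less in finite series;
- correlation of two series with the same ρ: √[(1+ρ²)/(1−ρ²)].

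At ρ = 0.5 the first is √(1.5/0.5) = 1.73 and the second √(1.25/0.75) = 1.29. At ρ = 0.9 they are √(1.9/0.1) = 4.36 (4.32 for 480 epochs) and √(1.81/0.19) = 3.09. The type I error of a nominal 5% test is 2[1 − Φ(1.96/ratio)]; a ratio of 1.73 gives 25.7% and a ratio of 4.32 gives 65.0%.

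**Simulation.** Random intercept only, independent residuals, 480 epochs per person, no true phase effect; 10, 20 or 40 persons. The correlation columns are for a per-person correlation near 0.9.

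| ρ (assumed) | Phase contrast: SE ratio | Phase contrast: type I error | Correlation SE ratio, device error autocorrelated | Correlation SE ratio, device error white noise |
|---|---|---|---|---|
| 0.5 | 1.73–1.77 | 25–28% | 1.28 | 1.13 |
| 0.8 | 2.97–3.03 | 49–53% | 2.08 | 1.60 |
| 0.9 | 4.11–4.32 | 64–66% | 3.04 | 2.15 |

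Separate runs with an assumed 30 persons gave 26–27%, 50–53% and 67% for the phase test. In the same 10-to-40-person simulations:
- mean bias had SE ratios of 0.97–1.06 and type I error of 3–6% at every ρ, because its SE comes from between-person variation;
- testing the phase contrast from one value per person gave type I error of 4–6% at every ρ.

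**What volume buys.** For 480 epochs, the effective number for a mean is 480/3 = 160 at ρ = 0.5 and 480/4.32² ≈ 26 at ρ = 0.9. For an overall mean over K persons, with between-person variance 0.25 and residual variance 1, the variance is (0.25 + 1/effective n)/K.
- With independent epochs, going from 480 to 5,760 changes the bracket from 0.2521 to 0.2502, so the SE falls by about 0.4%.
- At ρ = 0.9 (effective n of 26 and 304) it goes from 0.288 to 0.253, so the SE falls by about 6%.
- Doubling K lowers the SE by 1 − 1/√2 = 29%.

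Power for population-level questions therefore comes from families, not epochs.

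**Analyses with no epochs.** Saliva is taken at three times per session (section 3.3, Saliva Sample Collection). Questionnaires are given at no more than four time points (section 3.3, Psychosocial Questionnaires). The power statement covers these analyses too, but they have no large within-person data set to draw on.

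**The case against.** The strongest reply is that much of this is inferred from silence. A multi-level model can include random slopes and an autoregressive residual, and the plan excludes neither. Three stronger readings are tempting, and the documents do not support them.

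- *That the plan treats epochs within a patient as independent.* It never says so; it leaves the covariance unspecified. This stands as an objection, so the error rates above are conditional on a model that the plan has not stated.
- *That null effects in HR, SpO2 and HRV will be declared significant.* Section 5.1 defines epochs for comparing the two measurement systems, and the multi-level models are for bias and correlation/reliability. No epoch-level phase test is described, so the type I figures apply only if that model is carried over to the primary outcomes. The missing phase analysis is a gap in its own right, not proof of a wrong one.
- *That error bars are several times too narrow throughout.* Mean bias is not affected. A threefold error needs ρ of about 0.8 for contrasts and about 0.9 for correlations, and with white-noise device error the correlation ratio is only 2.15 at ρ = 0.9. The plan also states no interval or test for the per-person correlations, and autocorrelation does not invalidate them as descriptive values.

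None of this rescues the power paragraph, which expressly rests on within-person volume and extends to all planned analyses.

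**Conclusion.** The point holds in two parts. The power statement is wrong as written, whatever model is eventually fitted: it rests on repeated observations that are not independent, gives no number of families, effect size or variance, and covers hormone and questionnaire analyses that have only a few observations per person.

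The second part is conditional. With a patient intercept and independent residuals only, mean bias is safe. Standard errors for before/during/after contrasts on epochs would be about 1.7 to 4 times too small (type I error about 26% to 67% against a nominal 5%), and those for per-person correlations about 1.1 to 3 times too small. Those ranges rest on assumed lag-1 autocorrelation of 0.5 to 0.9 and an AR(1) shape. They show what leaving the covariance unspecified could cost; they are not properties of a stated analysis.

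**What to change.** 1. Delete the statement that within-person volume provides the power. Restate power or precision from the number of families, with an effect size and between-person variance, separately for physiology, hormones and questionnaires.
2. For HR, SpO2 and HRV across phases, specify one summary per person, phase and session before modelling. Alternatively, keep the epochs and add a random phase effect per person and an AR(1) residual within session; SPSS MIXED can fit this.
3. In the sensor-monitor agreement models, let bias and slope vary by person. Take any interval for a correlation from a person-level or block bootstrap.

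The cost is SAP wording and modest extra analysis work. Intervals will be wider, and the restated power may be well below the present claim.
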